9.5 Safety and Tolerability Assessments

Safety Analyses will be conducted on Safety population.

9.5.1 Adverse events

Adverse events (AEs) will be coded based upon the latest version of the Medical Dictionary for Regulatory Activities (MedDRA). Where changes in severity are recorded in the Case Report Form (CRF), each separate severity of the adverse event (AE) will be reported in the listings, only the most severe will be used in the summary tables. A pre-existing condition is defined as

an AE that starts before the subject has provided written informed consent and is ongoing at consent. A non-treatment emergent AE is defined as an AE which starts after informed consent but prior to dosing. A treatment-emergent AE is defined as an AE which occurs postdose or which is present prior to dosing and becomes more severe postdose.

All AEs will be listed. Treatment-emergent AEs will be summarized by treatment, severity and relationship to the study drug. The frequency (the number of AEs, the number of subjects experiencing an AE and the percentage of subjects experiencing an AE) of treatment-emergent AEs will be summarized by treatment, system organ class and preferred term. The summary and frequency AE tables will be presented for all causalities and those considered related to the study drug. Any serious AEs will be listed; this listing will include the reason the event was categorized as serious as well as relatedness.

9.5.2 Concomitant medication

Concomitant medication will be coded using the latest version of WHO drug dictionary. Concomitant medication will be listed.

9.5.3 Clinical laboratory parameters

All clinical chemistry, hematology and urinalysis data will be listed.

Additionally clinical chemistry, hematology and urinalysis data outside the local reference ranges will be listed.

Values for any clinical chemistry, hematology and urinalysis values outside the reference ranges will be flagged on the individual subject data listings.

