Safety: Safety laboratory parameters, vital signs, ECG parameters, and AEs will be listed and summarised using standard descriptive statistics.

Statistical: The primary and secondary PK and PD parameters will be log-transformed prior to analysis. The model will include subject as a random effect, with period, sequence, and treatment as fixed effects. For each PK and PD parameter, the comparison will be evaluated as the ratio of the least-squares geometric means of test formulation (LY2963016) to reference formulation (LANTUS). The estimate of the ratio of means between the 2 treatments and the corresponding 90% confidence interval will be provided. Descriptive statistics will be reported for all PK and PD parameters.

3. Table of Contents

Relative Bioavailability of LY2963016 to LANTUS® after Single-Dose Subcutaneous Administration in Healthy Chinese Subjects

Section	Page
1. Protocol I4L-MC-ABEF(b) Relative Bioavailability of LY2963016 to LANTUS® after Single-Dose Subcutaneous Administration in Healthy Chinese Subjects.....	1
2. Synopsis	2
3. Table of Contents.....	4
4. Abbreviations and Definitions.....	9
5. Introduction	12
5.1. General Introduction	12
5.2. Rationale and Justification for the Study	14
6. Objectives	15
6.1. Primary Objective	15
6.2. Secondary Objectives.....	15
7. Investigational Plan.....	16
7.1. Summary of Study Design.....	16
7.1.1. Screening Visit.....	16
7.1.2. Study Periods 1 and 2.....	16
7.1.3. Follow-up Visit	17
7.2. Discussion of Design and Control	17
7.3. Determination of Sample Size	17
8. Study Population.....	19
8.1. Criteria for Enrolment	19
8.1.1. Inclusion Criteria	19
8.1.2. Exclusion Criteria	20
8.2. Discontinuation	21
8.2.1. Discontinuation of Subjects.....	21
8.2.2. Discontinuation of Study Sites	22
8.2.3. Discontinuation of the Study	22
9. Treatment.....	23
9.1. Rationale for Selection of Dose	23
9.2. Investigational Product Formulations	23

9.3. Investigational Product Administration.....	23
9.4. Specific Restrictions/Requirements	24
9.5. Blinding	25
9.6. Concomitant Therapy	25
10. Pharmacokinetic, Pharmacodynamic, and Safety Data Collection.....	26
10.1. Pharmacokinetic and Pharmacodynamic Evaluations.....	26
10.1.1. Samples for Pharmacokinetic and Pharmacodynamic Measurements	26
10.1.2. Bioanalysis.....	26
10.1.3. Pharmacodynamic Evaluations (Glucose Clamp Procedure).....	26
10.2. Samples for Standard Laboratory Testing	27
10.3. Safety Evaluations.....	28
10.3.1. Safety Measures	28

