12.1.7.2. Statistical Evaluation of Safety

Safety parameters that will be assessed include safety laboratory parameters, vital signs, and ECGs. The parameters will be listed, and summarised using standard descriptive statistics. Additional analysis will be performed if warranted upon review of the data.

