Attachment 1. Protocol ABEF Study Schedule

Study Schedule Protocol I4L-MC-ABEF

Procedure	Screen ^a	Euglycaemic Clamp Procedure Periods 1 and 2 ^b				Discharge
	Within 4 weeks prior to Day -1	Day -1 Pre-Clamp	Day 1 Pre-Clamp	Begin Day 1, End on Day 2	Day 2 Post-Clamp	Between 7 and 14 Days of End of Period 2 or Early Discontinuation
Informed consent	X					
Medical history	X					
Height	X					
Serum pregnancy test	X	X ^c				X
Urine ethanol and drug screen	X					
Hepatitis B and HIV test	X					
FSH (if applicable)	X					
OGTT	X					
ECG	X		X		X	X
Randomization		Period 1				
Physical examination	X		X ^d		X ^d	X
Vital signs ^e (supine)	X		X		X	X
Clinical laboratory tests ^f	X	X				X
Subject admission to CRU		X				
Weight	X	X ^g				
Glucose clamp procedures				X ^h		
Blood sampling for PK ⁱ				-0.5 (predose), 0 (predose), 0.5, 1, 2, 3, 4, 6, 9, 12, 15, 18, 21 hr	24 hr	
C-peptide sampling ⁱ				-0.5 (predose), 0 (predose), 0.5, 1, 2, 3, 4, 6, 9, 12, 15, 18, 21 hr	24 hr	
LANTUS or LY2963016 administration (0.5 U/kg single dose SC)				X		
Subject Discharge from CRU					X	

Abbreviations: CRU = clinical research unit; ECG = electrocardiogram; FSH = follicle-stimulating hormone; HIV = human immunodeficiency virus; hr = hour(s); PK = pharmacokinetics; SC = subcutaneous; OGTT = oral glucose tolerance test.

- a Subjects who are not enrolled within 4 weeks of screening may be subjected to additional medical assessments and clinical laboratory tests prior to study entry.
- b The interval between treatment administrations (washout) will be at least 7 days.
- c Women of childbearing potential must have a negative serum pregnancy test ≤ 3 days prior to Day 1 of each period.
- d Abbreviated physical examinations may be performed pre- and post-clamp at each period.
- e Vital signs of supine pulse rate and supine blood pressure will be routinely measured. Body temperature will be measured on Day 1 of each period. During the clamp procedure, supine blood pressure and/or pulse rate may be measured as clinically indicated. Additional vital signs may be measured during each study visit, if warranted and agreed upon between Lilly and the investigator.

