9. STATISTICAL METHODOLOGY

9.1 General Considerations

Data listings will be provided for all data that is databased. Summary statistics and statistical analysis will only be presented for data where detailed in this SAP. For continuous data, summary statistics will include the arithmetic mean, arithmetic standard deviation (SD), median, min, max and N; for log-normal data (e.g. the PK parameters: AUCs and the maximum drug concentration [C_{max}]) the geometric mean and geometric coefficient of variation (CV%) will also be presented. For categorical data, frequency count and percentages will be presented. Data listings will be provided for all subjects up to the point of withdrawal, with any subjects excluded from the relevant population highlighted. Summary statistics and statistical analyses will generally only be performed for subjects included in the relevant analysis population. For the calculation of summary statistics and statistical analysis, unrounded data will be used.

Data analysis will be performed using SAS[®] Version 9.4 or greater.

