9.5.4 Vital signs

Vital signs will be listed for individual subjects.

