9.5.5 Electrocardiogram (ECG)

The ECG data will be listed for individual subjects.

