9.5.7 Other assessments

All other safety assessments not detailed in this section will be listed but not summarized or statistically analyzed.

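### The SAP drops the laboratory, vital-sign and ECG summaries and the firm tRmax evaluation that the protocol promises, yet Section 11 declares no changes

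*SAP*

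**What the plan says.** **Safety data, protocol.** The Synopsis states: "Safety laboratory parameters, vital signs, ECG parameters, and AEs will be listed and summarised using standard descriptive statistics". Section 12.1.7.2, which covers laboratory parameters, vital signs and ECGs, repeats the commitment: "The parameters will be listed, and summarised using standard descriptive statistics".

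**Safety data, SAP.** Section 9.5.3: "All clinical chemistry, hematology and urinalysis data will be listed", with an extra listing of out-of-range values and flags for them. Section 9.5.4: "Vital signs will be listed for individual subjects". Section 9.5.5: "The ECG data will be listed for individual subjects". No summary is described in any of the three. Section 9.1 adds: "Summary statistics and statistical analysis will only be presented for data where detailed in this SAP".

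**tRmax.** Protocol 12.1.5.2 makes a firm statement that tRmax will be evaluated nonparametrically. SAP 9.4.1 still derives tRmax. SAP 9.4.2 mentions its analysis only as one example of exploratory work that may be done.

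**Disclosure.** SAP Section 3 says the SAP supersedes the protocol's statistical content and that substantial differences will be identified. It reports that Version 2 updates Sections 7, 9.3.2 and 9.4.2 because of protocol errors, without saying what changed in 9.4.2 and without mentioning 9.5. Section 11 then states that nothing differs from the protocol-specified analyses.

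**The concern.** Safety and tolerability, and comparison of PD responses, are both secondary objectives. An analyst who follows the SAP exactly will produce no table of means or changes for pulse, blood pressure or ECG measures. A modest shift after one product would have to be noticed by reading individual listings.

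For tRmax, the decision whether to compare the products, and by what method, can be taken after the data of an open-label study have been seen. Pre-specification is meant to prevent that.

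Section 11 also tells a reader of the study report that there is nothing to look for. On these items that statement is wrong.

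**Working it through.** No power, variance or error-rate calculation bears on this point. The check is a comparison of text followed by a count.

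**Step 1. Commitments compared**

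| Item | Protocol | SAP | Difference declared in SAP Section 11? |
|---|---|---|---|
| Laboratory | List and summarise (Synopsis, 12.1.7.2) | List, with out-of-range listing and flags (9.5.3) | No |
| Vital signs | List and summarise (same) | List (9.5.4) | No |
| ECG | List and summarise (same) | List (9.5.5) | No |
| AEs | List and summarise (Synopsis) | List and summarise (9.5.1) | No difference |
| tRmax | Nonparametric evaluation, firm (12.1.5.2) | Optional, exploratory, no method (9.4.2) | No |

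The Synopsis promises summaries for 4 safety data types and the SAP provides 1, so 4 − 1 = 3 are missing. The Synopsis names 3 PD parameters (Rmax, Gtot, tRmax). Two keep a firm analysis and one does not.

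**Step 2. Does anything else in the SAP restore the summaries?** Section 9.1 lists generic statistics for continuous data, but it also limits summaries to data for which the SAP details them, so the generic list cannot fill the gap. Section 9.5.6 summarises blood glucose and C-peptide, not laboratory panels, vital signs or ECGs. Section 9.5.7 says "All other safety assessments not detailed in this section will be listed but not summarized or statistically analyzed". It covers only assessments not already detailed, so it does not govern these three, but it shows the same listings-only approach.

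**Step 3. Does anything in the protocol make its commitment conditional?** The proviso about event frequency is in 12.1.7.1, on AEs and symptoms. It does not attach to 12.1.7.2.

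**Step 4. Data affected.** Inputs:
- Protocol Attachment 1 schedules vital signs and ECG at Day 1 pre-clamp and Day 2 post-clamp in each of 2 periods. Footnote e confirms the measures: "Vital signs of supine pulse rate and supine blood pressure will be routinely measured".
- The target number of completers is 40 in Protocol 7.3 and 52 in SAP Section 7, so both are used.

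Vital signs and ECG, per measure:
- records per subject = 2 times × 2 periods = 4
- total = 40 × 4 = 160 to 52 × 4 = 208
- per product = 40 × 2 = 80 to 52 × 2 = 104, which is 40 to 52 pre/post pairs per product

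Laboratory: screening 1 + Day -1 in 2 periods 2 + follow-up 1 = 4 scheduled samples per subject, of which 2 are central and 2 local. None falls on Day 1 or Day 2, so no between-product laboratory claim is made.

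tRmax: one value per product per completer gives 40 to 52 within-subject pairs.

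**The case against.** The case for leaving the SAP alone has several parts.

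- **Clinically important findings have another route.** Protocol 10.3.2 requires significant ECG, laboratory and vital-sign findings that lead to a diagnosis to be reported. Treatment-emergent AEs are tabulated by treatment, and out-of-range laboratory values are flagged. This is true and limits the harm. It does not detect small average shifts, and vital signs and ECGs have no out-of-range listing.
- **Record counts overstate the information.** Half of the 80 to 104 records per product are taken before dosing, so only 40 to 52 are post-dose. That is correct; the pre-dose records serve as the baseline. The counts describe volume, not impact. The Safety population could also exceed the completers: if 60 subjects had full data, 60 × 4 = 240.
- **The protocol's tRmax sentence is itself loose.** It names no test, and it speaks of evaluating tRmax rather than comparing products. The Synopsis also describes log-transformation of PD parameters generally, while listing tRmax among them. Both points stand, and they are further reason for the SAP to settle the method. They do not make the protocol's commitment optional. The protocol's allowance for exploratory analysis of PD time parameters is a separate sentence.
- **The SAP supersedes the protocol, and Section 3 mentions 9.4.2.** Only substantial differences must be identified, and whether dropped summaries count as substantial is a judgement. But Section 11 makes an unqualified statement, and that statement is inaccurate. Naming 9.4.2 without saying what changed is not disclosure, and 9.5 is not named.
- **The table shells have not been seen and may contain the summaries.** That is possible. They would then conflict with SAP 9.1, so the SAP text would still need correcting.

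**Conclusion.** The concern holds. Read as written, the SAP omits descriptive summaries for three of the four safety data types the Synopsis commits to, downgrades one of three PD parameters from a firm to an optional analysis, and states in Section 11 that nothing changed. The effect is confined to secondary safety and PD reporting; inference on AUC(0-24) and Cmax is untouched. It should be corrected, but it does not threaten the trial's main conclusion.

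The counts assume 40 to 52 completers with every scheduled vital-sign and ECG record, and evaluable tRmax in both periods. The conclusion about what the SAP omits does not depend on those counts. The SAP was approved in May 2019 but cites only the original protocol and Amendment (a), so a difference between protocol versions may explain the mismatch. It would not resolve it, because the current documents disagree.

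**What to change.** 1. **SAP 9.5.4 and 9.5.5:** add descriptive summaries of vital signs and ECG by treatment and scheduled time (pre- and post-clamp in each period).
2. **SAP 9.5.3:** add descriptive laboratory summaries by visit, keeping central results (screening, follow-up) separate from local results (Day -1), with no between-product comparison.
3. **SAP 9.4.2:** make a nonparametric tRmax comparison firm and name the method, for example the Wilcoxon signed-rank approach that 9.3.2 already applies to tmax.
4. **SAP Section 11:** list and justify any departure that is kept, including listings-only reporting if that is intended, and say what Version 2 changed in 9.4.2.
5. **SAP Section 3:** cite the current protocol version. For Amendment (c), which moved HIV testing to a local laboratory, this is a citation update. The content of Amendment (b) is not shown and should be checked.

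The cost is SAP wording, a few standard tables and one test already specified for another parameter. No new data are needed.

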9.5.4 Vital signs

Vital signs will be listed for individual subjects.

9.5.5 Electrocardiogram (ECG)

The ECG data will be listed for individual subjects.

9.5.6 Glucose Monitoring and Hypoglycaemia Reporting

Hypoglycemic events will be appropriately recorded in the CRF. In the case of a hypoglycemic event, the actual blood glucose value, if measured, will be recorded in the CRF, together with any treatments administered. Each category of hypoglycemic event (defined in Section 10.3.2.1 of the Protocol) will be listed and summarized by treatment.

Blood glucose and C-peptide levels will be listed for individual patients and summarized by group.

9.5.7 Other assessments

All other safety assessments not detailed in this section will be listed but not summarized or statistically analyzed.

9.5.8 Safety and Tolerability Statistical Methodology

No inferential statistical analyses are planned.

10. INTERIM ANALYSES

No interim statistical analyses are planned.

11. CHANGES FROM THE PROTOCOL SPECIFIED STATISTICAL ANALYSES

There were no changes from the protocol specified statistical analyses.

13. DATA PRESENTATION

13.1 Derived Parameters

Individual derived parameters (e.g. PK parameters) and appropriate summary statistics will be reported to three significant figures. Observed concentration data, e.g. C_{max} , should be reported as received. Observed time data, e.g. t_{max} , should be reported as received. N and percentage values should be reported as whole numbers. Median values should be treated as an observed parameter and reported to the same number of decimal places as minimum and maximum values.

13.2 Missing Data

Missing data will not be displayed in listings.

13.3 Insufficient Data for Presentation

Some of the TFLs may not have sufficient numbers of subjects or data for presentation. If this occurs, the blank TFL shell will be presented with a message printed in the centre of the table, such as, "No serious adverse events occurred for this study."

Leo Document ID = 5fc9adfe-95d3-48d4-84f7-154d49bbfb0

Approver: PPD

Approval Date & Time: 03-May-2019 08:18:46 GMT

Signature meaning: Approved

Approver: PPD

Approval Date & Time: 06-May-2019 08:37:20 GMT

Signature meaning: Approved
